5.2.1.2 Sample Data Collection

All samples sent to the Blood Processing Core (BPC) will be barcoded, with data entered and stored in the Labmatrix utilized by the BPC. This is a secure program, with access to Labmatrix limited to defined [name] lab personnel, who are issued individual user accounts. Installation of Labmatrix is limited to computers specified by [name]. These computers all have a password restricted login screen.

Labmatrix creates a unique barcode ID for every sample and sample box, which cannot be traced back to patients without Labmatrix access. The data recorded for each sample includes the patient ID, name, trial name/protocol number, time drawn, cycle time point, dose, material type, as well as box and freezer location. Patient demographics associated with the clinical center

patient number are provided in the system. For each sample, there are notes associated with the processing method (delay in sample processing, storage conditions on the ward, etc.).

5.2.1.3 Sample Storage and Destruction

Barcoded samples are stored in barcoded boxes in a locked freezer at either -20 or -80°C according to stability requirements. These freezers are located onsite in the BPC and offsite at NCI Frederick Central Repository Services in Frederick, MD. Visitors to the laboratory are required to be accompanied by laboratory staff at all times.

Access to stored clinical samples is restricted. Samples will be stored until requested by a researcher named on the protocol. All requests are monitored and tracked in Labmatrix. All researchers are required to sign a form stating that the samples are only to be used for research purposes associated with this trial (as per the IRB approved protocol) and that any unused samples must be returned to the BPC. It is the responsibility of the NCI Principal Investigator to ensure that the samples requested are being used in a manner consistent with IRB approval.

Following completion of this study, samples will remain in storage as detailed above. Access to these samples will only be granted following IRB approval of an additional protocol, granting the rights to use the material.

Sample barcodes are linked to patient demographics and limited clinical information. This information will only be provided to investigators listed on this protocol, via registered use of the Labmatrix. It is critical that the sample remains linked to patient information such as race, age, dates of diagnosis and death, and histological information about the tumor, in order to correlate genotype with these variables.

5.2.2 NCI-Frederick Leidos Biomedical, Inc. Laboratory

Blood and tissue collected during the course of this study will follow storage, handling and labeling procedures to ensure that security, confidentiality and sample integrity are maintained. All samples (blood or tissue) are tracked by distinct identification labels that include a unique patient identifier and date of specimen collection. Thus, samples will be coded and linked, with access to personal data restricted to the study investigators.

All cryopreserved samples are tracked for freezer location and storage criteria. All samples are stored in a locked freezer at -70°C according to stability requirements. These freezers are located offsite at NCI-Frederick, at the Leidos Biomedical, Inc. Lab in Frederick, MD. Samples will be stored until requested by a researcher named on the protocol. All use and requests for use will be recorded by the Leidos Biomedical, Inc. Lab. Any unused samples must be returned.

Some samples as indicated below may be stored in monitored freezers/refrigerators in the investigator's laboratory at specified temperatures with alarm systems in place.

At the termination of this protocol, samples will remain in storage as detailed above. If additional studies are to be performed on any samples retaining patient identifiers, obtained during the conduct of this trial, a Request to Conduct Research for Stored Human Samples Specimens, or Data Collected in a Terminated NIH-IRB Protocol will be submitted. Otherwise, access to these samples will only be granted following IRB approval of an additional protocol, granting the rights to use the material. If specimens are to be discarded at any point, they will be disposed of in accordance with the environmental protection laws, regulations and guidelines of the Federal Government and the State of Maryland.

5.2.3 Women's Malignancies Branch (formerly [name] Laboratory)

Barcoded samples will be processed and stored by the Blood Processing Core (BPC) immediately after collection, and will remain with the BPC until requested for research use by the laboratory for planned analyses.

5.2.4 [name] Laboratory, NIAID

Access to patient identifying information will be restricted to appropriately trained members of the lab; samples will be deidentified by the lab before transfer to the [name] laboratory. Samples will be processed immediately by the [name] laboratory using validated SOPs in order to ensure specimen quality. All laboratory personnel will be trained to adhere to SOPs and will be monitored for high-quality performance. Using a computerized inventory system and a backup hardcopy process, all specimen collection and processing steps will be documented and the specific location of each specimen will be tracked. Each new specimen collected will be assigned a unique barcode identifier that can be linked to the original specimen collected and other relevant information within the inventory system. After processing, samples will not be stored in the [name] lab, but will be transferred back to the Women's Malignancies Branch (WMB) for storage.

6 DATA COLLECTION AND EVALUATION

6.1 DATA COLLECTION

The PI will be responsible for overseeing entry of data into a 21 CFR Part 11-compliant data capture system provided by the NCI CCR and ensuring data accuracy, consistency and timeliness. The principal investigator, associate investigators/research nurses and/or a contracted data manager will assist with the data management efforts. Primary and final analyzed data will have identifiers so that research data can be attributed to an individual human subject participant.

All adverse events will be collected as required in accordance with FDA regulations.

All adverse events, including clinically significant abnormal findings on laboratory evaluations, regardless of severity, will be followed until return to baseline or stabilization of event. Document AEs from the first study intervention, Study Day 0, through 30 days after the agent/intervention was last administered. Beyond 30 days after the last intervention, only adverse events which are serious and related to the study intervention need to be recorded.

An abnormal laboratory value will be recorded in the database as an AE **only** if the laboratory abnormality is characterized by any of the following:

- Results in discontinuation from the study
- Is associated with clinical signs or symptoms
- Requires treatment or any other therapeutic intervention
- Is associated with death or another serious adverse event, including hospitalization.
- Is judged by the Investigator to be of significant clinical impact
- If any abnormal laboratory result is considered clinically significant, the investigator will provide details about the action taken with respect to the test drug and about the patient's outcome.

End of study procedures: Data will be stored according to HHS, FDA regulations and NIH Intramural Records Retention Schedule as applicable.

Loss or destruction of data: Should we become aware that a major breach in our plan to protect subject confidentiality and trial data has occurred, this will be reported expeditiously per requirements in section [7.2.1](#).

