3.2 DRUG ADMINISTRATION

Monocytes are collected, elutriated and mixed with interferons according to [Appendix B](#).

The cell product is delivered to the inpatient ward, and infused within 4 hours after preparation. The cell product in 250 mL is infused via the intraperitoneal catheter/port over 30-60 min +/- 10 min.

After 2 cycles, per physician discretion, the infusion can be given as an outpatient in the day hospital/infusion center.

The administration is repeated every 28 days +/- 7 days to accommodate for holidays, inclement weather, or other scheduling conflicts.

Interactions between interferon gamma-1b and other drugs have not been fully evaluated. Caution should be exercised when administering interferon gamma-1b in combination with other potentially myelosuppressive agent. Preclinical studies in rodents using species-specific interferon-gamma have demonstrated a decrease in hepatic microsomal cytochrome P-450 concentrations. This could potentially lead to a depression of the hepatic metabolism of certain drugs that utilize this degradative pathway.

Peginterferon alfa-2b inhibits CYP1A2 and CYP2D6 activity. Monitor for potential increased toxicities of drugs metabolized by CYP1A2 and/or CYP2D6 with a low therapeutic index or a narrow therapeutic range when they are administered concomitantly with peginterferon alfa-2b.

Patients will continue therapy until documentation of progressive disease, limiting toxicity, intercurrent medical issues, or patient withdrawal

Participants will be contacted remotely or assessed in person at least once weekly during the first cycle of treatment. Subsequent follow up will be at least monthly, with the start of each new cycle, and then during follow up according to the defined schedule (see Study Calendar, Section [3.4](#)).

Pre-cycle and off-treatment AE assessments will be done at a scheduled clinic visit. Post-therapy follow-up assessments will be performed within 30 days of stopping study treatment over the phone or at a clinic visit.

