3.3 DOSE MODIFICATIONS

3.3.1 General Management of Toxicities

- In the case of toxicity, appropriate medical treatment should be used (including anti-emetics, anti-diarrheals, etc.).
- Once a patient has a dose reduction for toxicity, the dose will not be increased.
- Participants continuing to experience toxicity at the off study visit may be contacted for additional assessments until the toxicity has resolved or is deemed irreversible.
- For AEs that are unrelated to the study drugs, study drug may be held for up to 14 days at the discretion of the PI.

3.3.2 General Recommendations for Dose Modification and Management of Hematologic Adverse Events occurring after the DLT period

Table 2. Dose Modification and Management of Hematologic Adverse Events

Observation	Action
-------------	--------

Absolute neutrophil count (ANC) \geq 1000/mcL AND Platelets \geq 75,000/mcL AND Hemoglobin \geq 8 g/dL	No interruption.
ANC < 1000/mcL OR Platelets < 75,000/mcL OR Hemoglobin < 8 g/dL	
On first occurrence, hold treatment for up to 14 days until ANC \geq 1000/mcL, platelets \geq 75,000/mcL, and hemoglobin \geq 8 g/dL. Initiate appropriate medical therapy (per Section 3.3.2.1) and no change in dose upon re-initiation.
 
On second occurrence, hold treatment for up to 14 days until ANC \geq 1000/mcL, platelets \geq 75,000/mcL, and hemoglobin \geq 8 g/dL. Initiate appropriate medical therapy (per Section 3.3.2.1). Treatment may be restarted at one dose level (DL) lower for the drug(s) causing the toxicity.
 
Patients whose counts have not recovered to ANC \geq 1000/mcL, platelets \geq 75,000/mcL, and hemoglobin \geq 8 g/dL after 14 days should be removed from treatment.

Grade 4 hematologic AE	
On first occurrence, hold treatment for up to 14 days until ANC \geq 1000/mcL, platelets \geq 75,000/mcL, and hemoglobin \geq 8 g/dL. Initiate appropriate medical therapy (per Section 3.3.2.1). Treatment may be restarted at one DL lower for the drug(s) causing the toxicity.
 
On second occurrence, discontinue all three experimental agents and follow the patient for adverse events as described in section 3.5 until resolution/stabilization of toxicity.

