3.3.2.1 Hematologic toxicities

- Treatment may be delayed for a maximum of 2 weeks after holding the treatment for toxicities that develop and do not resolve as defined above (exemptions: lymphopenia, or leukopenia in the absence of grade 3 or higher neutropenia).

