3.3.2.4 Anemia

- Symptomatic anemia should be treated with red blood cell transfusion and is recommended if the hemoglobin falls below 8 g/dL or the patient is symptomatic.
- The initiation of erythropoietic therapy for the management of chemotherapy-induced anemia follows the American Society of Hematology/ASCO clinical practice guidelines (<http://www.asco.org>).

3.3.3 General Recommendations for Dose Modification and Management of Non-Hematologic Adverse Events

- The management of general AEs not otherwise specified should be as per **Table 3**.
- At the discretion of the investigator, the study drugs or monocytes may be held or dose modified independently if the observed toxicity is attributed to only one of the agents, while the patient continues to receive the agent(s) not associated with the observed toxicity.
- Dose modifications for nausea, vomiting, and diarrhea will be made only if they are refractory to treatment. The time a given drug is held should not exceed 14 days.
- Asymptomatic electrolyte abnormalities with optimal repletion will not require dose reduction if resolution to grade 1 or less is documented within 72 hours.

Table 3. General Management of Adverse Events (Non-Hematologic)

Observation	Action
Grade 1 or 2 AEs resolves promptly (within 48 hours) with supportive care	Maintain dose level (DL)
Any \geq grade 3 non-hematologic $>72\text{h}$ (excluding those mentioned in Section 3.1.1 , Dosing Limiting Toxicity)	During DLT evaluation period: Patient will be removed from treatment At any other time Hold study regimen for up to 14 days until toxicity resolves to \leq grade 1. Treatment may be restarted at one DL lower according to PI discretion.

Any grade 2 non-hematologic AE lasting > 7 days despite maximal support.	Hold study regimen for up to 14 days until toxicity resolves to \leq grade 1. Treatment may be restarted at one DL lower according to PI discretion Patients whose toxicity has not resolved after 14 days will be removed from treatment.
--	--

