8.2 ASSESSMENT OF SAFETY EVENTS

AE information collected will include event description, date of onset, assessment of severity and relationship to study product and alternate etiology (if not related to study product), date of resolution of the event, seriousness and outcome. The assessment of severity and relationship to the study product will be done only by those with the training and authority to make a diagnosis and listed on the Form FDA 1572 as the site principal investigator or sub-investigator. AEs occurring during the collection and reporting period will be documented appropriately regardless of relationship. AEs will be followed through resolution.

SAEs will be:

- Assessed for severity and relationship to study product and alternate etiology (if not related to study product) by a licensed study physician listed on the Form FDA 1572 as the site principal investigator or sub-investigator.
- Recorded on the appropriate SAE report form, the medical record and captured in the clinical database.
- Followed through resolution by a licensed study physician listed on the Form FDA 1572 as the site principal investigator or sub-investigator.

For timeframe of recording adverse events, please refer to section [6.1](#). All serious adverse events recorded from the time of first investigational product administration must be reported to the sponsor with the exception of any listed in section [8.4](#).

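### Full adverse event recording under Section 6.1 can close while a patient who is held for toxicity, and never re-dosed, is still on protocol therapy

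*Combined protocol and SAP*

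**What the plan says.** **Recording period.** Section 6.1 documents AEs from Study Day 0 "through 30 days after the agent/intervention was last administered". After that the rule narrows: "Beyond 30 days after the last intervention, only adverse events which are serious and related to the study intervention need to be recorded". Section 8.2 sets no period of its own: "For timeframe of recording adverse events, please refer to section" 6.1.

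**Dosing and holds.** Section 3.2 states: "The administration is repeated every 28 days +/- 7 days". Section 3.3.2.1 states: "Treatment may be delayed for a maximum of 2 weeks after holding the treatment for toxicities". Under Table 2 (Section 3.3.2), patients whose counts have not recovered "after 14 days should be removed from treatment". Table 3 (Section 3.3.3), in its grade 2 row, states: "Patients whose toxicity has not resolved after 14 days will be removed from treatment". The row for grade 3 or higher events outside the DLT period has the same 14-day limit but does not spell out removal.

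**Follow-up anchors.** Section 3.4 footnote 2 and Section 3.5 time the post-therapy visit from the last dose, at about one month. Section 3.2 times post-therapy assessments from the stopping of study treatment. It also plans an AE assessment at a clinic visit when the patient comes off treatment.

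**Events already on record.** Section 6.1 says these, "regardless of severity, will be followed until return to baseline or stabilization of event".

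**The concern.** The recording period hangs on the last infusion alone, yet treatment status continues past it. A patient can be between infusions, on hold and still on protocol therapy when the 30 days run out. If she is then removed without another infusion, new events from the end of the hold fall under the narrower rule.

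The loss would be selective, because it arises only in patients who stop after an unresolved toxicity hold. Those patients are informative about whether repeated cycles at Dose Level 4 can be tolerated. Section 3.1.2 combines the expansion patients with the earlier patients at the maximum tolerated dose (MTD) to improve the safety estimates, and Section 10 puts that group at 16. One incomplete record is 1/16, or 6.25%, of it.

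**Working it through.** The plan gives no figure for this, so the check is calendar arithmetic. Days are counted from the last infusion as day 1.

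**Inputs**
- Full recording: 30 days after the last infusion (6.1)
- Interval between infusions: 28 days, with 7 days either way for scheduling (3.2)
- Longest hold: 14 days (3.3.2, 3.3.2.1, 3.3.3)
- Start of the hold: not stated

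**Formulas**
- Close of full recording: C = 1 + 30 = day 31
- End of a full hold: E = start of hold + 14
- Gap: G = max(0, E − C)

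**Reading A: the hold runs from the date the next infusion is due**

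| Due date | End of hold | Gap |
|---|---|---|
| 1 + 28 − 7 = day 22 | day 36 | 5 days |
| 1 + 28 = day 29 | day 43 | 12 days (days 32 to 43) |
| 1 + 28 + 7 = day 36 | day 50 | 19 days |

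**Reading B: the hold runs from toxicity onset on day s**

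The gap is zero when s + 14 ≤ 31, that is, when s ≤ 17. A hold starting on day 18 gives 1 day, on day 22 gives 5 days, and on day 29 gives 12 days.

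**Effect of re-dosing.** Recording runs without a break to 30 days after the last administration, so another infusion closes the gap retrospectively. Take a new, related, non-serious event on day 35. If the patient is re-dosed on day 40, the period extends to day 40 + 30 = day 70 and the event must be recorded. If she is removed on day 43 without re-dosing, it need not be. The obligation turns on what happens after the event.

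**Mismatch of anchors.** If stopping treatment in 3.2 means the removal decision, the 3.2 follow-up limit for a patient removed on day 43 is day 43 + 30 = day 73. The last-dose anchor gives day 31. The difference is 73 − 31 = 42 days. The off-treatment assessment in 3.2 would then ask about events that 6.1 does not require to be entered.

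**What is and is not lost in the gap**
- Toxicity that caused the hold: kept (6.1, 3.4 footnote 2, 8.2)
- New event, serious and related: kept (6.1)
- Death: captured through the stopping rule (3.3.4), the off-study criteria (3.5.2) and progression-free survival (6.3.6)
- New event that is non-serious or unrelated: recording not required

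**DLT window.** It is 28 days (3.1), inside the 30-day period.

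**The case against.** The strongest reply is that counting 30 days from last exposure is the protocol's usual convention, and that the informative events survive it. The toxicity behind the hold is followed. Serious related events have no time limit. Section 3.1 halts enrollment for IRB and FDA evaluation if a related DLT-like event occurs in a later cycle. Section 3.2 already plans an assessment when treatment ends. The rule also says what need not be recorded, not what must be left out, so staff who expect to re-dose may well record the event anyway. The 19-day figure combines the toxicity hold with an allowance meant for scheduling conflicts.

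Most of this stands, and it narrows the point. It does not remove it. A planned assessment does not create a duty to record when 8.2 sends the reader back to 6.1, and optional recording is not uniform recording. Several DLT categories in 3.1.1, such as prolonged grade 3 fatigue, can be non-serious.

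Reading B is also open on the text. Against it, treatment is one infusion per cycle, so a hold that expires before the next due date delays nothing. Even so, holds starting after day 17 run past day 31.

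The wording of 6.1 leaves one further escape: it refers to the agent or intervention, so a later apheresis or protocol biopsy might restart the clock. Apheresis serves to prepare an infusion, so it would not ordinarily occur in a patient on hold.

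**Conclusion.** The point holds in limited form. Full recording can end before the patient leaves protocol therapy. The gap is 12 days on the nominal schedule if the hold runs from the due date, 5 to 19 days if the scheduling allowance is added, and zero if the hold runs from an onset by day 17. It requires a hold that lasts past day 31 and no further infusion. The documents do not allow the number of such patients to be estimated.

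A reader might infer more, and the documents do not support it:
- **That all patients removed for toxicity are affected.** Table 3 removes some directly during the DLT period with no hold, and the length of any gap depends on an unstated starting point.
- **That the period is wholly unrecorded, or that an unrelated death would go unnoticed.** Sections 3.3.4, 3.5.2 and 6.3.6 capture deaths without requiring that they be related. At most the AE entry for a death is affected.
- **That the MTD is in doubt.** The DLT window lies inside the recording period, and Section 3.1.3 reports that escalation has concluded.

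What remains is possible selective incompleteness of the repeat-cycle safety tables, and a conflict of anchors between 3.2 and Sections 6.1, 3.4 and 3.5. It should be corrected, but it does not threaten the primary objective.

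**What to change.** In Section 6.1, require all AEs, whatever their seriousness or relationship, to be recorded through the later of (a) 30 days after the last infusion and (b) the off-treatment visit planned in Section 3.2. Apply the narrower rule only after that date. Reconcile the anchors in 3.2, 3.4 footnote 2 and 3.5 with this end date, and state the day from which a toxicity hold is counted. This review takes no position on which day that should be, and no dose, hold length or removal rule needs to change.

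The cost is one sentence in 6.1, matching edits elsewhere, and about 12 more days of recording (up to 19) in the patients removed after a full hold. The information can be collected at a visit that already exists.
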